Healthcare providers will use ePoct+ for the assessment, diagnosis and management of all sick children 0 – 59 months of age (i.e. only excluding those coming for routine immunisation or monitoring visits and not reported to be unwell). In case a child comes back to the facility during the same disease episode, ePoct+ can be used to manage the child in the same way as during the baseline visit, as the algorithm takes into account duration of symptoms and previous treatments provided.

MedAL-R, the front-end application developed by Unisanté/Wavemind to implement ePoct+ is available for Android tablet or PC. The application can be deployed in health facilities in a standalone mode or a multi-device mode to facilitate the collaboration of several healthcare providers and storage of information in the patient's medical records. In the context of this study, MedAL-R will be deployed on tablets. The choice of a standalone / multi-device setting will depend on discussions with the country MoHs.

The clinical algorithm will be adapted to reflect national guidelines for the management of children 0-59 months of age in primary care. An expert group will be established and consulted in each country using a Delphi method approach and / or nominal group technique to validate the clinical algorithm.

The adaptation of ePoct+ will be done using MedAL-C, the back-end software developed by Unisanté/Wavemind to manage, reference, modify and deploy the different versions of the clinical algorithm into MedAL-R. Recommendations on use of additional point of care laboratory and diagnostic test use, such as malaria or haemoglobin, will be incorporated into the algorithm if routinely available at the targeted health facilities. Before the start of the study, ePoct+ will be reviewed and validated by national key experts in child health. MedAL-C allows an interactive visualization of the clinical algorithm and therefore clinicians without any IT programming skills can modify the decision trees to release a new version of the clinical algorithm. However, the clinical algorithm will not be updated for the duration of the study, except for technical reason (patches).

Training

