6.5 Participant timeline

6.5.1 Pragmatic cluster RCT

The study flowchart is presented in Fig. 5. Research assistants will screen and recruit participants in the waiting area prior to consultation as outlined in Section 10.3. Following informed consent and enrolment, research assistants (RAs) will record participant name,

address and contact details (including personal and alternate contacts) for Day 7 and Day 28 follow-up, basic sociodemographic details, reason for attendance and care-seeking. This will be collected from the caregiver before consultation, except in critical / emergency cases who will be seen immediately by the healthcare provider. The clinical consultation will be conducted by healthcare providers who have been advised to use the devices as described above according to the facility allocation.

After the consultation, the RA will use extract information from the clinical records from the caregiver (child health card and / or referral note), and / or from clinic ledgers or medical records. Information will be extracted and recorded on the final diagnosis, oxygen saturation and results of laboratory investigations (if performed), prescribed medication with dosage, referral or follow-up advice and the usage of the pulse oximeter device and/or CDSA (if applicable). Research assistants will seek clarification from healthcare providers in cases where the diagnosis is not clear from the records.

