6.1.3.2 Proportion of children prescribed a diagnosis-appropriate antibiotic

Appropriateness of antibiotic prescription in relation to diagnosis will be evaluated as:

- ξ Proportion of children who received a diagnosis for which a systemic antibiotic was indicated and a systemic antibiotic was prescribed
- ξ Proportion of children who received a diagnosis for which a systemic antibiotic was not indicated and systemic antibiotic was prescribed

- ξ Proportion of children who received first-line (or second-line) antibiotics according to recommendations for IMCI diagnoses for which specific antibiotic(s) are indicated

Only children with a diagnosis for which a systemic antibiotic was indicated will be counted in the denominator for the first proportion, only children with a diagnosis for which a systemic antibiotic was not indicated will be counted in the denominator of the second proportion, and only children who received an IMCI diagnosis requiring specific antibiotics will be counted in the denominator of the third proportion.

Diagnoses will be classified according to whether systemic antibiotics are indicated, based on IMCI and other relevant national guidelines as used for the CDSA, using the structured data entry and free text if feasible. Diagnosis classification will be defined in a separate document.

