6.2 Analysis Methods

6.2.1 Analytical Methods

Outcomes will be described by arm using summary statistics. In particular, counts and percentages will be used for binary variables and reported with one decimal place; mean and standard deviation (SD) or median (IQR) for continuous variables depending on their distribution. Mean and median will be displayed with one decimal place and SD and IQR will be presented with two decimal places.

The two primary outcomes will be assessed using a random effects logistic regression model with the cluster included as a random effect. If convergence issues arise due to sparse data, clusters may be dropped or combined to higher grouping level (e.g. district).

Results will be reported with odds ratios, risk differences and their associated 95% confidence intervals (CI). The control arm will be used as reference category.

Secondary outcomes and other binary outcomes of interest will be evaluated in the same way.

Other continuous outcomes of interest will be assessed using random effects linear regression model with the cluster included as a random effect. Results will be reported in terms of adjusted mean differences between arms with associated 95% CIs.

Modelling of secondary outcomes will be performed if numbers allow.

For interim analyses and DMC analyses, only the two primary outcomes will be presented. Modelling will not be performed and results will be reported in terms of summary statistics only.

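### In the Tanzanian CDSA comparison, antibiotic appropriateness is modelled between arms within groups set by a diagnosis that the CDSA itself guides

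*Protocol*

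**What the plan says.** SAP 6.1.3.2 defines three proportions. The first is the "Proportion of children who received a diagnosis for which a systemic antibiotic was indicated and a systemic antibiotic was prescribed". Each has its own denominator:

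- First: "Only children with a diagnosis for which a systemic antibiotic was indicated will be counted in the denominator for the first proportion".
- Second: "only children with a diagnosis for which a systemic antibiotic was not indicated will be counted in the denominator of the second proportion".
- Third: "only children who received an IMCI diagnosis requiring specific antibiotics will be counted in the denominator of the third proportion".

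Whether a diagnosis calls for a systemic antibiotic is decided "based on IMCI and other relevant national guidelines as used for the CDSA", with the classification left to a separate document.

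The diagnosis comes from the consultation records. Protocol 6.5.1 says of the period after the consultation: "Information will be extracted and recorded on the final diagnosis". In the CDSA arm, which exists only in Tanzania, Protocol 6.3 says: "Healthcare providers will use ePoct+ for the assessment, diagnosis and management of all sick children". Protocol 8.1.2 and 10.1 add that the tool gives automated recommendations on diagnosis, which the provider may accept or reject.

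SAP 6.2.1 sets out a random-effects logistic model for the primary outcomes, with odds ratios, risk differences and control as reference, and then says: "Secondary outcomes and other binary outcomes of interest will be evaluated in the same way".

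**The concern.** Randomising facilities makes the children recruited in each arm comparable. It does not make comparable the subsets who receive a particular diagnosis, once the intervention acts on the diagnosis. The CDSA is meant to change how children are assessed and classified. A child with the same illness may fall in the indicated denominator in one arm and the not-indicated denominator in the other.

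A between-arm effect estimate on these proportions then cannot be read as an effect on prescribing. Part of it may come only from how children were labelled. Antimicrobial prescription is named in the protocol's objectives, and the protocol summary lists an appropriate-antibiotic measure among its important secondary and other outcomes. Readers will want to interpret the contrast.

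**Working it through.** The plan states no power, sample size or expected value for this outcome, so there is no figure to reproduce. The check has two parts.

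**1. Do the documents break the link between arm and denominator?**

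- All three denominators in SAP 6.1.3.2 depend on the diagnosis the child received, which is known only after the consultation and hence after allocation.
- The separate document named there classifies diagnoses as needing an antibiotic or not. It is not described as re-deriving each child's diagnosis from signs recorded alike in every arm.
- The plan avoids this problem elsewhere. Protocol 6.4.2 puts all enrolled children in the denominator of the referral-admission primary outcome, because a referred-only denominator could look good in routine care when too few children are referred. SAP 6.1.2.3 and 6.1.2.6 also use all recruited children, with the referred-only proportion as an addition. SAP 6.1.3.2 has no all-recruited version.
- SAP 6.1.3.1 (any antibiotic, all recruited children) is free of the problem but does not address appropriateness.

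**2. What can labelling alone do?** All inputs here are assumptions. Let each arm have N = 1,000 children and R = 600 prescriptions. Let L be the number given an antibiotic-requiring diagnosis, all of them treated.

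- Indicated and prescribed = L / L = 100% for any L.
- Not indicated and prescribed = (R − L) / (N − L).

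| L | Calculation | Not indicated and prescribed |
|---|---|---|
| 200 | 400 / 800 | 50.0% |
| 350 | 250 / 650 | 38.5% |
| 500 | 100 / 500 | 20.0% |

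Two arms with L = 200 and L = 500 differ by 30 points on the second proportion with the same prescribing. The first proportion shows nothing, because every labelled child is treated by assumption.

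A second illustration lets both proportions move. Take 84% prescribing (the routine-care figure from a study of another decision tool, cited in Protocol 3.2). Assume that 20% of children truly need an antibiotic (within the 15–30% that Protocol 6.3 gives for suspected pneumonia, used as a stand-in) and that 90% of these are treated.

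- Prescriptions in children with a true need: 200 × 0.90 = 180.
- Prescriptions in the other 800: 840 − 180 = 660, or 660 / 800 = 82.5%.
- Labels correct: first proportion 180 / 200 = 90.0%, second 82.5%.
- Half of the 660 (330) carry an antibiotic-requiring label: first proportion (180 + 330) / (200 + 330) = 510 / 530 = 96.2%; second (660 − 330) / (800 − 330) = 330 / 470 = 70.2%.

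The same children are treated in both cases.

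**Check on one possible remedy.** Counting children prescribed an antibiotic without an antibiotic-requiring diagnosis over all recruited children gives (600 − 200) / 1,000 = 40% against (600 − 500) / 1,000 = 10%. The 30-point gap remains, because the numerator still depends on the label.

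**The case against.** The best defence is that the outcome does what its name says: it describes agreement between the recorded diagnosis and the treatment, which fits the guideline-adherence objective. Total prescribing is measured over all recruited children in SAP 6.1.3.1. Correctness of classification is examined in the service provision assessment (Protocol 6.4.3). This justifies keeping the three proportions as descriptions. It does not justify effect estimates against control. The service provision assessment is exploratory and covers six facilities per arm, about 600 observations per arm.

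Several limits on the point stand in full:

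- **Direction.** A reader might infer that over-diagnosis in control would be scored as appropriate, so that the contrast favours control. The documents do not support this. Protocol 3.2 describes under-classification of severity, and Protocol 6.3 worries about missed suspected pneumonia. If control providers under-label and still prescribe, the bias reverses.
- **Shared standard.** A reader might instead infer that scoring by the CDSA's guidelines tilts the result towards that arm. The standard is IMCI and national guidance, and every arm receives refresher training on it (Protocol 6.3). The documents do not settle the net effect.
- **Size.** The 33–87% correct classification cited in Protocol 3.2 is a range across observational studies. It is neither a difference between trial arms nor a rate of antibiotic-requiring labels, so it cannot support a shift from 200 to 500.
- **Reach.** The mechanism does not extend to India alone or to pulse oximetry alone against control, since only the CDSA is described as guiding diagnosis in this way.
- **Rank.** Protocol 6.4.2 and SAP 3.1.4 list this as an other outcome of interest. It is outside the testing procedure for the primary outcomes and cannot make the trial positive.

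**Conclusion.** The concern holds in a limited form. For the Tanzanian CDSA comparison, and for pooled analyses that include that arm, the three proportions condition on a post-allocation diagnosis that the intervention guides. Their denominators can be expected to differ by arm, and the modelled contrast cannot separate labelling from prescribing.

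Neither direction nor size can be derived, because the documents give no diagnosis frequencies by arm. The 50% against 20% result rests wholly on assumed figures. It shows that a large difference is possible with identical prescribing, not that one is expected. The primary and listed secondary outcomes are unaffected. The change is worth making because it is cheap and follows the denominator logic that the plan already uses for referral.

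**What to change.** In SAP 6.1.3.2, for contrasts involving the CDSA arm:

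1. Report the three diagnosis-conditioned proportions by arm as descriptions, without causal effect estimates, and exempt them from the general modelling sentence in SAP 6.2.1.
2. Beside them, report how often each diagnosis class was recorded in each arm, over all recruited children.
3. Make the between-arm comparison on systemic antibiotic prescribing within caregiver-reported presentation groups fixed before the consultation: cough or difficulty breathing, fever, diarrhoea, other. State how children with more than one symptom are assigned, and how emergency cases seen before their caregiver is interviewed (Protocol 6.5.1) are handled.
4. If a figure for antibiotics prescribed without an antibiotic-requiring diagnosis is given over all recruited children, label it as descriptive only.

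The cost is SAP wording and a small amount of extra tabulation. Caregiver-reported presentation is already collected on Day 0 (Protocol 8.1.1), and SAP 4.2 already uses pre-consultation signs alongside provider diagnosis to assess adherence. The downside is that presentation groups are coarser than diagnoses and do not measure appropriateness directly, so the descriptive proportions are still needed.

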6.4 Outcomes

6.4.1 Pilot phase

Progression to the definitive trial will be based on the following outcomes:

- 80% of healthcare providers adhering to critical steps of the pulse oximetry use guidelines (combination of WHO and manufacturer guidelines provided as part of intervention), assessed using the SPA observation in pilot facilities
- 80% of eligible children recruited
- 90% of caregivers reachable by phone on Day 7 for outcome assessment

If these outcomes are not met during the pilot phase, the research steering committee will review and advise on adjustments and progress to the definitive trial.

Furthermore, the following outcomes will be assessed in order to verify sample size assumptions:

- Attendance rate of eligible children per month attending study
- Primary outcome proportions in routine care

If a deviation from the original assumptions are substantial, sample size calculations and recruitment strategies will be reviewed and modified if necessary.

6.4.2 Pragmatic cluster RCT

Two primary outcomes will be assessed in order to improve the ability to detect a difference between intervention and control arms, given the relatively low occurrence of severe outcomes at primary care level:

- Proportion of children with a severe complication (death or secondary hospitalisation) by Day 7
 - Secondary hospitalisation refers to any delayed hospitalisation (occurring at any point greater than 24 hours after Day 0 consultation) and any hospitalisation occurring without referral. The denominator is all enrolled children

- Proportion of children admitted to hospital within 24 hours of the Day 0 primary care consultation and as a result of a referral
 - This is used as a proxy for 'appropriate referral' of children, as those with severe disease should generally be admitted to hospital. The denominator for this outcome is also all children enrolled in the study, rather than only referred children. This is because the proportion of referred children that are admitted may be high in routine care, in the context of an inappropriately low referral rate. The aim of the intervention is therefore to increase the overall referral rate of children with severe disease. Hospital admission is chosen as the proxy of severe disease rather than using primary care classification of severe disease, as there are inadequacies in the classification of severe disease in routine practice

The trial will be interpreted as positive if either primary outcome is positive with no indication of harm from non-significant outcomes. This will be assessed separately in India and Tanzania and will also be assessed across the two countries for the sub-group of children presenting with cough or difficulty breathing.

We anticipate that we will see a greater effect on the 'appropriate referral' outcome, given that increasing detection and referral of children with severe disease is the focus of the intervention, and that morbidity and mortality among children with severe disease is highly contingent on quality of care at hospital level, which is not the focus of the intervention. Whilst hospital admission is still contingent on factors beyond the remit of the intervention (e.g. on caregiver completion of referral and hospital bed availability), it is not dependent on quality of care during hospital admission.

Secondary outcomes:

- Proportion of children with severe complication (death or secondary hospitalisation) by Day 28
- Proportion of children cured (defined as caregiver reported recovery from illness) at Day 7 follow-up
- Proportion of children referred by a primary care healthcare provider to a higher level of care (either to a hospital or to an inpatient part of a larger primary healthcare facility) at Day 0 consultation

Proportion of children who completed referral, as reported at day 7 follow-up
Other outcomes of interest – hypoxaemia (in intervention arms only)

- Proportion of children with severe ($\text{SpO}_2 < 90\%$), moderate ($\text{SpO}_2 90 - 91\%$) and mild hypoxaemia ($\text{SpO}_2 92 - 93\%$), adjusted for sites at high altitude
- Proportion of children with hypoxaemia (according to differing cut-offs) with severe complication
- Proportion of children with severe hypoxaemia not meeting any other clinical criteria for severe disease

- Proportion of children referred with hypoxaemia who receive oxygen at hospital

Other outcomes of interest – referral and follow-up

- Proportion of children with non-severe disease referred to a higher level of care on Day 0
- Average length of stay (in days) of children admitted to hospital
- Proportion of children attending scheduled follow-up at the same facility by Day 7
- Proportion of children presenting for unscheduled follow-up to any health facility by Day 7

Other outcomes of interest – antimicrobial prescription

- Proportion of children prescribed an antibiotic at Day 0
- Proportion of children prescribed a diagnosis-appropriate antibiotic
- Proportion of febrile children tested for malaria at Day 0
- Proportion of malaria positive children prescribed an antimalarial
- Proportion of malaria negative children prescribed an antimalarial
- Proportion of untested children prescribed an antimalarial

Sub-groups for analysis of primary and secondary outcomes:

- Age (under 2 months, 2 – 12 months, 13 – 59 months)
- Sex
- Presentation with cough / difficulty breathing

Other factors for exploratory analyses

- Additional sociodemographic characteristics urban / rural location, distance from health facility, key household indicators such as maternal age and education
- Main complaint / symptom categories (including cough / difficulty breathing, fever, diarrhoea and other) and time since onset of symptoms
- Alternative hypoxaemia cut-offs
- Healthcare provider severity classification
- Facility and health system factors – type of facility, healthcare provider qualification and previous training

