6.1.1 General definitions

Day 7 / Day 28 assessment

Day 7 / Day 28 assessment refers to information reported by the caregiver after Day 0 and recorded in Day 7 / Day 28 forms. Data collected as part of unscheduled visits are also integrated in these forms.

If multiple successful follow-up assessments for the same child are recorded within Day7 or Day28 databases, the most recent follow-up assessment within each database will be used. To limit potential recall bias, assessments conducted far beyond the expected follow-up time will be dropped. This will be 30 and 60 days from Day 0 for Day 7 and Day 28 respectively.

Death

A child will be considered deceased if, from Day 7 / Day 28 assessment, his/her status at the time of follow-up is “deceased”. In case of implausible death date (i.e. prior to enrolment date), death will be handled as follow:

- ξ if death date is recorded at Day7 follow-up, death will be assumed to be within 7 days of Day0
- ξ if death date is not recorded at Day7 follow-up but only at Day28 follow-up, death will be assumed to be after 7 days of Day0 but within 28 days.

Hospitalisation

A child will be considered hospitalised if, from Day 7 / Day 28 assessment, he/she went to a hospital, was admitted overnight or if his/her status at the time of follow-up is “hospitalised”. In case of implausible hospitalisation date (i.e. prior to enrolment date), hospitalisation will be handled as follow:

- ξ if hospitalisation date is recorded at Day7 follow-up, hospitalisation will be assumed to be within 7 days but after 24hrs of Day0
- ξ if hospitalisation date is not recorded at Day7 follow-up but only at Day28 follow-up, hospitalisation will be assumed to be after 7 days of Day0 but within 28 days.

Hospitalisation within 24hrs of Day0

For the purpose of primary analysis, a child will be considered admitted to hospital 24hrs of Day0 consultation if the date of hospitalisation is the same as Day0 date or is one day after Day0 date.

Referral

A child will be considered to be referred (either to a hospital or to an inpatient part of a larger primary healthcare facility) if, at Day0, the caregiver confirms that the child was urgently referred or the research assistant confirms that an urgent referral advice was recorded for the child. If urgency is unknown from both sources, referral will be assumed to be urgent.¹

Antibiotics

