6.1.2 Health, hospitalisation and referral outcomes

6.1.2.1 Proportion of children with a severe complication by Day 7

Severe complication is defined as death or secondary hospitalisation. Secondary hospitalisation refers to any delayed hospitalisation (occurring at any point greater than 24hrs after the Day 0 consultation) and any hospitalisation occurring without a referral.

Information on death and hospitalisation will be taken, in order, from:

- ξ Day7 follow-up assessment
- ξ If Day7 follow-up assessment is missing, Day28 follow-up assessment

Death will be counted in the numerator if death date is within 7 days of Day0 (7th day included). Hospitalisation will be counted in the numerator if the child was not referred at Day0 or hospital admission date is within 7 days of Day0 (7th day included) but after 24hrs of Day0.

The denominator will be all children recruited. Children for whom no death and hospitalisation data are available or withdrew prematurely from the study will be assumed to be alive and not hospitalised by Day7.

6.1.2.2 Proportion of children with a severe complication by Day 28

Severe complication is defined as per the outcome above.

Information on death and hospitalisation will be taken, in order, from:

- ξ Day7 follow-up assessment
- ξ If Day7 follow-up assessment is missing or no outcomes were reported, Day28 follow-up assessment
- ξ If both Day7 and Day28 assessments are missing or no outcomes were reported, unscheduled visits (deaths only)

Death will be counted in the numerator if death date is within 28 days of Day0 (28th day included). Hospitalisation will be counted in the numerator if the child was not referred at Day0 or hospital admission date is within 28 days of Day0 (28th day included) but after 24hrs of Day0.

The denominator will be all children recruited. Children for whom no death and hospitalisation data are available or withdrew prematurely from the study will be assumed to be alive and not hospitalised by Day28.

6.1.2.3 Proportion of children admitted to hospital within 24 hours of Day 0 consultation and as a result of a referral

Information on hospitalisation will be taken, in order, from:

- ξ Day7 follow-up assessment
- ξ If Day7 follow-up assessment is missing, Day28 follow-up assessment

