Hospitalisation will be counted in the numerator only if the child received a referral advice (as per definition above) at Day0 and hospital admission date is within the end of the following day. The denominator will be all children recruited.

Additionally, the proportion will be calculated and reported using only children who were referred as denominator.

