6.2.4 Pre-planned Sensitivity Analyses

Sensitivity analyses on the primary outcomes are planned and will be conducted:

- ξ On first encounters, which will include only the first enrolment episode of each child during the study period (as some children may attend the facility on more than one occasion). Separate presentations are identifiable from Day0 form as the caregiver is asked whether the child attended previously and within 28 days. This is the minimum number of days required for the disease episode to be considered a new one and not a repeat visit.
- ξ Looking at different hospitalisation appropriateness (based on different definitions of primary and secondary hospitalisations). Same day (Day0), 3 days and 7 days from Day0 will be used as cut-offs for different primary and secondary hospitalisation definitions.
- ξ Looking at different referral definitions:
 - ο A child will be considered to be referred if, at Day0, caregiver confirms that the child was urgently referred *and* the research assistant confirms that an urgent referral advice was recorded for the child².
 - ο A child will be considered to be referred if, at Day0, the research assistant confirms that an urgent referral advice was recorded for the child. If urgency is unknown, referral will be assumed to be urgent.

Additionally, a set of sensitivity analyses on the primary outcomes shall be carried out in case of substantial missing data (e.g. >10%) to evaluate the impact of each method on the primary outcomes results and take them into account when interpreting the final analysis results. Planned methods will include:

- ξ Worst case scenario
- ξ Complete cases
- ξ Multiple imputations with chained equations [11, 12]

Details of the methods are provided in Section 6.3.

Sensitivity analyses will only be performed for the final statistical analysis and not for interim analyses and DMC reports.

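### Recorded referral decides whether a prompt admission counts as a severe complication or as appropriate hospitalisation, and no planned model of hospitalisation is free of that label

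*Protocol*

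**What the plan says.** Outcome 1 is death or secondary hospitalisation by Day 7. Protocol 6.4.2 counts delayed admissions as secondary, and also "any hospitalisation occurring without referral". SAP 6.1.2.1 repeats this ("and any hospitalisation occurring without a referral") and gives the counting rule: "Hospitalisation will be counted in the numerator if the child was not referred at Day0 or hospital admission date is within 7 days", the dated part applying to admissions later than 24 hours.

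Outcome 2 in Protocol 6.4.2 is the "Proportion of children admitted to hospital within 24 hours of the Day 0 primary care consultation and as a result of a referral". SAP 6.1.2.3 counts an admission "only if the child received a referral advice (as per definition above) at Day0" and if it falls by the end of the next day. SAP 6.1.1 treats an admission as within 24 hours "if the date of hospitalisation is the same as Day0 date or is one day after Day0 date". Both outcomes use all recruited children as denominator.

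On purpose, Protocol 6.4.2 says: "The aim of the intervention is therefore to increase the overall referral rate of children with severe disease". Under SAP 4.1 a favourable result on either primary outcome makes the trial positive for that arm; Protocol 6.4.2 adds that there should be no sign of harm.

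SAP 6.2.4 lists sensitivity analyses on first episodes, on timing ("Looking at different hospitalisation appropriateness (based on different definitions of primary and secondary hospitalisations", with same-day, 3-day and 7-day cut-offs), on the source of the referral record, and on missing data.

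**The concern.** Referral is the behaviour the intervention is meant to change, and it also decides which primary outcome a Day 0-1 admission falls into. If a surviving child is admitted that day or the next, recording a referral removes one event from outcome 1 and adds one to outcome 2. Both changes look favourable, so the no-harm condition gives no protection.

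SAP 3.5 describes the trial's aim as benefit in mortality and morbidity. A fall in outcome 1 would naturally be read that way, although part of it could reflect only how the child reached hospital or what was written down. The label does depend on records: in India urgent referral comes from the registry alone (footnote to SAP 6.1.1), and Protocol 8.1.1 notes that registry information there is often incomplete and provides study-specific forms for that reason.

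**Working it through.** **1. What an added referral does, by type of child**

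| Child who becomes referred | Outcome 1 | Outcome 2 |
|---|---|---|
| Would have been admitted on Day 0-1 anyway; survives | one fewer | one more |
| Would not otherwise have been admitted; now admitted on Day 0-1 | no change | one more |
| Still admitted only after the next day, by Day 7 | counted either way | not counted |
| Dies by Day 7 | counted either way | counted only if admitted on Day 0-1 |

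Only the first row is pure relabelling.

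**2. Do the planned analyses remove the label?**

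- Timing cut-offs: referral stays in the definition. The 3-day and 7-day versions lengthen the window in which it decides the classification, so outcome 1 depends on it more.
- Referral source: changes how the label is read and keeps it.
- First episodes and missing-data methods: same outcome definitions.
- Subgroup by referral (SAP 6.2.5): conditions on a post-randomisation variable, and outcome 2 is zero by definition in unreferred children.
- Deaths (SAP 6.5): label-free, but counts and percentages only.
- Cure at Day 7 (SAP 6.1.2.8): label-free and modelled if numbers allow, but it says nothing about hospitalisation, and children without Day 7 data are taken as cured.

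**3. Reproducing the design (Protocol 6.6.1, SAP 3.4)**

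Inputs: 80% power, alpha 0.05 (taken as two-sided), ICC 0.001, outcome 1 from 1.1% to 0.77%. The pooled two-proportion formula without continuity correction gives 13,351 children per arm before clustering. Design effect = 1 + (m - 1) x ICC.

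- Tanzania: 1 + 1,679 x 0.001 = 2.679; 13,351 x 2.679 = 35,767; / 1,680 = 21.3, so 22 clusters, as stated.
- India (initial): 1 + 509 x 0.001 = 1.509; 13,351 x 1.509 = 20,147; / 510 = 39.5, so 40 clusters, as stated.

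Effective size per arm: Tanzania 22 x 1,680 / 2.679 = 13,796; India with 60 clusters 60 x 510 / 1.509 = 20,278.

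**4. Size of pure relabelling**

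Let s be the share of outcome 1 events that are unreferred Day 0-1 admissions of survivors and become referred. The documents give no value; 10% to 30% is an assumption.

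Outcome 1 = 1.1% x (1 - s). Outcome 2 = 1.5% + 1.1% x s.

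Chance of significance = Phi{[d x sqrt(n) - z x sqrt(2 x pbar x (1 - pbar))] / sqrt(p1(1 - p1) + p2(1 - p2))}, where d is the absolute difference between p1 and p2, pbar is their mean, n is the effective size and z = 2.241 (two-sided 0.025).

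Example, Tanzania, s = 0.30: (0.0033 x 117.46 - 2.241 x 0.1361) / 0.1361 = 0.61, so 73%.

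| s | Outcome 1 | Fall (points) | Outcome 2 | Outcome 1 significant: Tanzania / India | Outcome 2 significant: Tanzania / India |
|---|---|---|---|---|---|
| 10% | 0.99% | 0.11 | 1.61% | 9% / 12% | 7% / 9% |
| 20% | 0.88% | 0.22 | 1.72% | 35% / 50% | 21% / 32% |
| 30% | 0.77% | 0.33 | 1.83% | 73% / 89% | 46% / 64% |

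In a simulation of both outcomes together, at least one is significant at 0.025 in 15%, 49% and 85% of trials in Tanzania and 20%, 66% and 96% in India. In children: Tanzania expects 36,960 x 1.1% = 407 outcome 1 events per control arm, so s = 10% is about 41 children and s = 30% about 122.

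Equal cluster sizes are assumed. SAP 4.1 lets outcome 1 be tested at 0.05 once outcome 2 passes, so its chance under the full procedure is somewhat higher than shown.

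**The case against.** An unreferred admission may be a true missed case, which is a sound reason to count it against the facility. That supports keeping the endpoint, but the component still measures referral practice, so a claim of better health needs separate support.

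The plan is also not blind to the problem. Both outcomes share a denominator and are reported with risk differences, so pure relabelling would show as equal and opposite shifts. Apart from referred, promptly admitted children who die by Day 7, the sum of the two is death or any counted admission. This stands, but the sum has no planned confidence interval. Deaths and cure add label-free information, and the planned referral rates would help show whether practice changed. A reader might infer that nothing in the plan could reveal relabelling; the documents do not support that.

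A reader might also infer that any rise in referral lowers outcome 1. It does not: Protocol 6.4.2 is directed at children whom low referral rates miss, and a newly referred child who would not otherwise have been admitted changes outcome 2 only.

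Finally, the targeted rise in outcome 2 (1.5% x 0.30 = 0.45 points) could be set against outcome 1 to suggest a fall of 0.45 / 1.1 = 41% by relabelling alone. That needs every extra referred admission to be a child who would have been admitted anyway, and at least 41% of outcome 1 events to be unreferred Day 0-1 admissions. Nothing in the documents establishes either.

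**Conclusion.** The point holds as a gap in the supporting analyses. It does not invalidate the primary outcomes. The two are coupled through recorded referral, relabelling moves both in the favourable direction, and no planned model of hospitalisation removes the label.

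The size is unknown. At 10% relabelled the effect is small (0.11 points, significant in roughly one trial in ten). At 30% it equals the whole design effect of 0.33 points. These figures rest on the assumed share, the planned control rates and ICC, equal cluster sizes, and nothing else differing between arms. They show why the share should be measured; they do not predict the trial's result.

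**What to change.** Keep both primary outcomes. In SAP 6.2.4 add by-arm models, using the primary model and reporting risk differences with 95% CIs, of:

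- (a) death or any hospitalisation by Day 7, regardless of referral;
- (b) death or hospitalisation after 24 hours and by Day 7, regardless of referral;
- (c) death alone by Day 7, numbers permitting.

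Also tabulate by arm how many outcome 1 events are unreferred Day 0-1 admissions.

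State in advance that a fall in outcome 1 will be interpreted as a health benefit in the light of the estimates and intervals for (b) and (c). Do not use a pass/fail rule on direction: with no true effect, (b) alone would point the favourable way about half the time. State too that (a) may rise if the intervention increases appropriate admission, so a rise is not in itself evidence of harm.

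Deaths, admissions and their dates are already collected whatever the referral status (SAP 3.8 and 6.1.1). The cost is a few extra models and one table, and possibly a more cautious reading of outcome 1. The documents give no death rate, so the precision of (c) cannot be judged in advance.
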